16.2 Visual Acuity (ETDRS)

VA will be measured at every study visit prior to the CAC. For Visit 4, it will be measured again post-CAC. Visual acuity (logMAR) will be summarized by treatment using the average of both eyes for each subject with quantitative summary statistics. The number of subjects with worsening of acuity of 10 letters or more from baseline will also be summarized with counts and with percentages based on the total number of subjects in each treatment group with responses. Results for VA will be presented in a data listing.

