10.3.1.4 VISIT 4 (Day 15 \pm 3): 10-Minutes Onset of Action CAC

- *Update of Medical/Medication History*
- *Adverse Event Query*
- *Urine Pregnancy Test (for females of childbearing potential)*
- *Visual Acuity Utilizing an ETDRS Chart:* A clinically significant visual acuity decrease (defined as an increase of 0.22 or greater in logMAR score) from Visit 1 will be considered an adverse event.
- *Pre-CAC Ocular Allergic Signs and Symptoms Assessment:* [REDACTED]
[REDACTED]

- Slit Lamp Biomicroscopy
- Investigational Product Instillation: [REDACTED]
[REDACTED]
[REDACTED]
- Conjunctival Allergen Challenge: [REDACTED]
[REDACTED]
- Post-CAC Ocular Allergic Signs and Symptoms Assessment: Assessment of itching will be made by the subject at 5(± 1), 10(± 1), 15(± 1), 20(± 1), 30(± 1), and 60(± 5) minutes following allergen challenge. [REDACTED]
[REDACTED] at 10(± 1), 15(± 1), 20(± 1), 30(± 1), and 60(± 5) minutes post-challenge (**Appendix 2**).
- Exit Visual Acuity Utilizing an ETDRS Chart: A clinically significant visual acuity decrease (defined as an increase of 0.22 or greater in logMAR score) from Visit 1 will be considered an adverse event.
- Exit Slit Lamp Biomicroscopy
- IOP Measurement: Intraocular Pressure (IOP) will be measured in each eye by contact tonometry. An IOP of ≥ 30 mmHg or an increase of 10 mmHg over baseline (Visit 1) will be considered an Adverse Event.
- Dilated Fundoscopy
- [REDACTED]
- Adverse Event Query
- Study Exit

If a female has a positive pregnancy test during the study, then the investigator will notify Ora immediately. The investigator will follow-up and document the outcome of the pregnancy and provide a copy of documentation to the Sponsor. The investigator will retain these reports together with the subject's source documents and will provide a copy of all documentation to Ora.

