9.1 Unit of Analysis

The subject will be considered the unit of analysis for all variables with exceptions of slit-lamp biomicroscopy and dilated fundus examination. For the variables using subject as the unit of the analysis, the average of both eyes of each subject will be used for statistical summaries and analyses in cases where data are collected for each eye. For slit-lamp biomicroscopy and dilated fundus examination results, the eye will be the unit of analysis and summaries will be provided for all eyes combined.

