9.3 Definition of Baseline

For the primary efficacy variable (ocular itching scores at 10(± 1), 15(± 1), and 20(± 1) minutes post-CAC), baseline will refer to the time-relevant measure at Visit 2 (e.g., ocular itching at 10 minutes post-CAC at Visit 2 will be the baseline for ocular itching at 10 minutes post-CAC at Visits 3 and 4).

For all safety variables, baseline is defined as the last measurement prior to the first dose of study medication. Change from baseline will be calculated as follow-up visit minus baseline visit.

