Additional summaries of AEs will be provided showing the number of AEs and the number and percentage of subjects who experienced at least one AE. These summaries will be presented at the subject and event level by SOC and PT. If a subject reports the same PT multiple times within the same SOC, that PT will only be reported once within that SOC. As with the PT, if a subject reports multiple conditions within the same SOC, that SOC will only be reported once. In the summary, SOC will be listed in ascending alphabetical order; PTs will be listed in order of descending frequency for all subjects within each SOC. These summaries will be presented for ocular and non-ocular AEs separately and include the following:

- All AEs;
- All TEAEs;
- All TEAEs suspected to be related to the IP;
- All SAEs;
- All TEAEs by maximal severity; and

Subject listings will be provided for all adverse events, serious adverse events, adverse events leading to death and adverse events leading to study treatment discontinuation.

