16.4 Intraocular Pressure (IOP)

[figure not shown]
IOP will be measured at Visits 1 (post-CAC®) and 4 (post-CAC) and will be summarized by treatment using the average of both eyes for each subject with quantitative summary statistics. At Visit 4, an IOP of ≥ 30 mmHg or an increase of 10 mmHg over baseline (Visit 1) will be considered an AE; the number of subjects meeting this criteria will be summarized with counts and with percentages based on the total number of subjects in each treatment group with responses. IOP will be listed for each eye at each visit.

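### The two-eye averaging default in SAP 9.1 reaches the visual acuity worsening count in SAP 16.2, so a loss in one eye is halved before it meets the 10-letter cut-off (low priority)

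*SAP*

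**What the plan says.** SAP 9.1 sets a general rule: "The subject will be considered the unit of analysis for all variables with exceptions of slit-lamp biomicroscopy and dilated fundus examination". For variables under that rule, "the average of both eyes of each subject will be used for statistical summaries and analyses in cases where data are collected for each eye". Visual acuity is not among the exceptions. It is collected by eye: the entry criterion in Protocol 7.3 applies to each eye separately.

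SAP 16.2 plans two summaries. The first is a quantitative summary of logMAR, for which the two-eye average is stated outright. The second is the count: "The number of subjects with worsening of acuity of 10 letters or more from baseline will also be summarized with counts". The sentence with the count names no eye and makes no exception to 9.1. SAP 9.3 fixes the reference: "For all safety variables, baseline is defined as the last measurement prior to the first dose of study medication". For acuity that is normally the Visit 3 reading. Acuity is read twice at Visit 4, before the challenge and at exit.

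SAP 16.4 is built the same way for intraocular pressure: an averaged quantitative summary, then a count in which "the number of subjects meeting this criteria will be summarized with counts and with percentages", again with no eye named.

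**The concern.** An average suits a summary of level. A count of subjects past a worsening threshold has a different purpose, which is to pick out individuals with a notable loss. Dosing is bilateral, but an ocular reaction can still be confined to one eye or be much worse in one. If the two eyes are averaged first, the fellow eye dilutes the loss and the effective threshold for one-eye damage doubles. The 10-letter count is the only acuity-worsening count in the visible text of the SAP, so a reader of the report could take a count of zero as showing that no eye lost 10 letters, when it shows only that no subject's mean did.

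**Working it through.** The plan gives no figure to reproduce. The check is arithmetic on its own rule, followed by a noise calculation on stated assumptions.

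**Step 1: does the average govern the count?** SAP 9.1 covers all variables but two and reaches all statistical summaries of per-eye data. SAP 16.2 restates the average for one summary and sets no other rule for the other. The default therefore applies to the count.

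**Step 2: the effect.** Inputs: cut-off 10 letters (SAP 16.2); averaging (SAP 9.1). Let L be the letters lost in the worse eye and f the letters lost in the fellow eye (negative for a gain). The subject is counted if (L + f)/2 ≥ 10, that is, L ≥ 20 − f.

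| One-eye loss L (f = 0) | Two-eye average | Counted under the average? | Counted if either eye qualifies? |
|---|---|---|---|
| 10 | 5.0 | no | yes |
| 15 | 7.5 | no | yes |
| 19 | 9.5 | no | yes |
| 20 | 10.0 | yes | yes |

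If the fellow eye gains 5 letters the worse eye must lose 20 + 5 = 25; if it loses 5, the worse eye must lose 20 − 5 = 15. The loss is exactly halved only when the fellow eye is unchanged.

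**Step 3: what an either-eye count costs.** The documents give neither the SD of change in acuity nor the between-eye correlation. Assume the two changes are bivariate normal with per-eye SD s of 3 to 6 letters and correlation r of 0 to 0.5. The SD of the average is s·√((1 + r)/2).

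Worked case, s = 6, r = 0, no true loss:
- One eye: P(change ≥ 10) = P(Z ≥ 10/6) = 0.0478.
- Either eye: 1 − (1 − 0.0478)² = 0.0933; times 50 = 4.7.
- Average: SD = 6 × √0.5 = 4.243; P(Z ≥ 10/4.243) = 0.0092; times 50 = 0.46.

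Each row below compares the two rules under the same assumptions. The planned arm size is about 50.

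| s, r | False flags per 50 per reading: average | False flags: either eye | True 15-letter one-eye loss counted: average | Counted: either eye |
|---|---|---|---|---|
| 3, 0 | 0.0001 | 0.04 | 12% | 95% |
| 3, 0.5 | 0.003 | 0.04 | 17% | 95% |
| 6, 0 | 0.46 | 4.7 | 28% | 81% |
| 6, 0.5 | 1.4 | 4.2 | 32% | 80% |

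The either-eye count is much more sensitive to a one-eye loss in every row. Its noise cost is negligible at s = 3 and substantial at s = 6.

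**Step 4: intraocular pressure.** The rule in SAP 9.1 reaches the SAP 16.4 count in the same way. A rise of 15 mmHg in one eye with none in the other averages (15 + 0)/2 = 7.5, below the 10 mmHg increase in that section.

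**The case against.** The strongest reply is that the averaging of the count is inferred. In SAP 16.2 the average is attached to the logMAR sentence; the next sentence changes both the unit and the statistic, and a programmer could code it as either eye. That stands as a description of the wording. It does not remove the point, because coding it that way would depart from SAP 9.1 without a stated exception, and two programmers could then report different counts.

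It can also be said that bilateral dosing makes a two-eye measure defensible and that an either-eye count is noisier. Both are true. The first supports the average for the quantitative summary more than for a threshold count. The second is a real cost, shown above; it falls on all arms, so the vehicle arm gives its background rate.

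A reader might go further and infer that the SAP drops the protocol's Visit 4 criterion, a rise "defined as an increase of 0.22 or greater in logMAR score) from Visit 1 will be considered an adverse event", or that it uses the wrong baseline. The documents do not support this. The protocol passage tells the investigator when to record an adverse event; it does not promise a table. Protocol 12.12 asks only for descriptive summaries of acuity, with changes and shifts where applicable. The last pre-dose value is a legitimate safety baseline. The pressure count is no precedent for a Visit 1 reference, because Visit 1 is the only scheduled pre-dose pressure reading.

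Nor is the difference between 10 letters and 0.22 logMAR a shown inconsistency: comparing them needs a letter-to-logMAR conversion that the documents do not give.

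**Conclusion.** The point holds as a cheap improvement of low priority. Under the plan's own default, with a stable fellow eye, one-eye losses of 10 to 19 letters are left out of the SAP 16.2 count and 20 letters are needed to enter it. That result is arithmetic and rests only on SAP 9.1 applying where 16.2 is silent. The sensitivity and false-flag figures rest on the assumed SD, correlation and normality, and serve only to show the trade-off.

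It would be wrong to conclude that such losses go unreported. Acuity is a secondary safety variable with no inferential testing. Losses meeting the protocol's Visit 4 criterion are recorded as adverse events and so enter the tables of SAP 16.1, where "These summaries will be presented at the subject and event level by SOC and PT", and the adverse event listings. Acuity itself is listed. What is lost is a threshold count that is sensitive to one eye. The contents of the SAP's table list are not visible, so the finding is limited to the text of 9.1, 16.2 and 16.4.

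**What to change.** In SAP 16.2, state that the two-eye average applies only to the quantitative logMAR summary. State that a subject is counted as worsened when either eye meets the SAP's existing 10-letter criterion against that eye's SAP baseline, reported separately for the Visit 4 pre-challenge and exit readings. Note this in SAP 9.1 as an exception. Give the pressure count in SAP 16.4 the same eye rule, leaving its criterion as it is. No cut-off or reference visit changes.

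The cost is a few lines of SAP text and minor programming on data already collected. The downside is the extra noise flags shown above, so the counts should be presented by arm and read against vehicle.

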16.3 Slit-Lamp Biomicroscopy Examination

A slit-lamp biomicroscopy examination will be performed at each visit prior to the CAC and again post-CAC for Visit 4, and will consist of the examination of the following items:

- Eyelid;
- Conjunctiva;
- Cornea;
- Lens; and
- Anterior Chamber.

The results will be graded as normal, abnormal not clinically significant (NCS) or abnormal clinically significant (CS). The results will be summarized using counts and percentages for each treatment group for all eyes combined. Percentages will be based on the number of subjects eyes in each treatment

group with responses. A shift table will also be produced showing changes from baseline in slit-lamp examination results for each treatment and post-baseline assessment.

A subject listing of the slit-lamp biomicroscopy parameters will also be produced.

16.4 Intraocular Pressure (IOP)

[figure not shown]
IOP will be measured at Visits 1 (post-CAC®) and 4 (post-CAC) and will be summarized by treatment using the average of both eyes for each subject with quantitative summary statistics. At Visit 4, an IOP of ≥ 30 mmHg or an increase of 10 mmHg over baseline (Visit 1) will be considered an AE; the number of subjects meeting this criteria will be summarized with counts and with percentages based on the total number of subjects in each treatment group with responses. IOP will be listed for each eye at each visit.

16.5 Dilated Fundoscopy Examination

Dilated fundus examinations will be performed at Visits 1 (post-CAC) and 4 (post-CAC). Counts and percentages of normal and abnormal results will be presented for all eyes combined by visit and treatment group for the following regions: vitreous, retina, macula, choroid, and optic nerve. Percentages will be based on the number of subject eyes in each treatment group with responses. A shift table will also be produced showing changes from baseline in dilated fundus examination results for each treatment and post-baseline assessment. Results will be listed for both eyes at each visit.

17. Interim Analyses

No interim analysis is planned for this study.

[figure not shown]

[figure not shown]
19. Revision History

[figure not shown]
Documentation of revision to the SAP will commence after approval of the Final version 1.0.

[figure not shown]
20. Tables

Tables that will be included in the topline delivery are shown in boldface font.

[figure not shown]

[figure not shown]

21. Listings

22. Figures
